9.4 Contraception and Restrictions

Male Subjects with Partners of Childbearing Potential

Male subjects who are sexually active with a partner of childbearing potential must use, with their partner, a condom plus an approved method of highly effective contraception from the time of informed consent until 111 days after IMP administration. This has been calculated based on 90 days (one cycle of spermatogenesis) plus 5 half-lives of the IMP. 5 half-lives have been calculated as 21 days based on the mean half-life of 98.138 h observed in healthy volunteers at a single dose of 225 mg.

The following methods are acceptable:

- Partner's use of combined (oestrogen and progestogen-containing) hormonal contraception associated with inhibition of ovulation:
 - oral
 - intravaginal
 - transdermal
- Partner's use of progestogen-only hormonal contraception associated with inhibition of ovulation:
 - oral
 - injectable/implantable
 - intrauterine hormone-releasing system
 - Partner's use of intrauterine device
- Vasectomised
- Partner's bilateral tubal occlusion

These contraception requirements are considered to be more conservative than the guidance issued by the Heads of Medicines Agency: Clinical Trials Facilitation Group [17].

Males with Partners of Non-childbearing Potential

There is a significant risk of drug exposure through the ejaculate (which also applies to vasectomised males) that might be harmful to sexual partners. Therefore, even if a male is sexually active with a partner of non-childbearing potential they will be required to use a condom from IMP administration until discharge from the study.

All Subjects

Alternatively, sexual abstinence is considered a highly effective method only if defined as refraining from heterosexual intercourse during the entire period of risk associated with the study treatments. The reliability of sexual abstinence needs to be evaluated in relation to the duration of the clinical trial and the preferred and usual lifestyle of the subject.

9.4.1 Sperm Donation

Male subjects should not donate sperm for the duration of the study and for 111 days after IMP administration.

9.5 Pregnancy

Subjects will be instructed that if their partner becomes pregnant during the study this should be reported to the investigator. The investigator should also be notified of pregnancy occurring during the study but confirmed after completion of the study. In the event that a subject's partner is subsequently found to be pregnant after the subject is included in the study, then consent will be sought from the partner and, if granted, any pregnancy will be followed and the status of mother and/or child(ren) will be reported to the sponsor after delivery.

A pregnancy notification form and follow-up will be completed.

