In study CRV431-103, there were no SAEs or deaths reported following treatment with 75 mg rencofilstat alone or in combination with 400 mg ketoconazole or 2 mg midazolam. One patient discontinued study participation due to a TEAE of elevated ALT/AST and subsequent COVID-19 infection. Twenty-eight AEs were recorded for 12 subjects. Investigators assessed 21 AEs as Grade 1, 6 AEs as Grade 2, and 1 AE as Grade 3. The grade 3 AE, elevated ALT, was considered unrelated to study drug and instead related to COVID-19 infection. TEAEs reported in 2 or more subjects were nausea (4 subjects [14.8%], diarrhoea, dizziness, headache, alanine aminotransferase increased, and aspartate aminotransferase increased (2 subjects [7.4%]). There were no findings or changes from baseline observed in any of the laboratory parameters (haematology, coagulation, blood chemistry, urinalysis), vital signs, pulse oximetry or ECG that were deemed to be clinically significant by the investigator.

In study CRV431-104, there was 1 AE related to clinically significant out-of-range vital signs (blood pressure increased) reported by 1 subject in the fed cohort. The AE was Grade 1 (mild) and judged by the Investigator as not related to study treatment.

Overall, rencofilstat was safe and well tolerated at all combinations tested to date in healthy subjects. There are no important identified risks or potential identified risks from the rencofilstat development program.

Non-clinical genotoxicity studies were all negative. These data presented a favourable safety profile for rencofilstat with acceptable safety margins that support the proposed clinical development program. No reproductive or developmental toxicity studies of rencofilstat have been performed as of the IB cut-off date of 01 Oct 2022. However, no females will take part in this study, and the male volunteers must agree to adhere to the contraception requirements defined in Section 9.4. No phototoxicity studies have been conducted on rencofilstat as of the IB cut-off date of 01 Oct 2022. Owing to the unavailability of phototoxicity data, subjects will be advised to minimise exposure to sunlight following dosing until discharge from the study (see Section 9.6).

All formulation excipients are United States Pharmacopeia (USP) grade or National Formulary (NF) grade and therefore have a Generally Recognised As Safe (GRAS) designation. Consequently, it is deemed safe to use in this study.

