18.5 Declaration of the End of the Study

The end of the study is defined as the last visit of the last subject (eg discharge from the study). Any changes to this definition will be notified as a substantial amendment (see Section 17.1).

The EC and MHRA should be notified of the conclusion of the study within 90 days of the end of the study, or within 15 days if the study is terminated early, clearly explaining the reasons for the termination.

The ARSAC Practitioner will also be notified of the end of trial or early termination of the trial within an appropriate timeframe.

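### Section 9.5 asks subjects to report partner pregnancies only if they occur during the study, which leaves about 74 to 90 of the protocol's 111 post-dose risk days without an instruction to notify

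*Protocol*

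**What the plan says.** **Risk period.** For men with a partner of childbearing potential, Protocol section 9.4 requires contraception "from the time of informed consent until 111 days after IMP administration". It gives the derivation: "This has been calculated based on 90 days (one cycle of spermatogenesis) plus 5 half-lives of the IMP", and "5 half-lives have been calculated as 21 days based on the mean half-life of 98.138 h observed in healthy volunteers". Section 9.4.1 uses the same limit: "Male subjects should not donate sperm for the duration of the study and for 111 days after IMP administration".

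**Reporting period.** Section 9.5 is narrower. Its first sentence is "Subjects will be instructed that if their partner becomes pregnant during the study this should be reported to the investigator". Its second is "The investigator should also be notified of pregnancy occurring during the study but confirmed after completion of the study". A third sentence deals with a partner found to be pregnant after the subject's inclusion: consent is sought and, if given, the pregnancy is followed and the outcome goes to the sponsor. The section closes by requiring a notification form and follow-up.

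**End of study.** Section 18.5 ends the study at the last subject's final visit, with discharge as its example. Section 14.3 stops adverse event recording at discharge from the study.

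**Background.** Section 6.4.1 records that "No reproductive or developmental toxicity studies of rencofilstat have been performed as of the IB cut-off date of 01 Oct 2022".

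**The concern.** The protocol sets a period in which a conception is of concern, but instructs the subject to report only over a much shorter one. The second sentence of 9.5 relaxes the date of confirmation, not the date of conception. A conception on Day 60, say, is inside the period that 9.4 guards and outside the instruction in 9.5.

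The text does not allow *during the study* to be read as running to day 111. Section 9.4.1 names the study's duration and the 111 days as two separate periods, and section 9.6 does the same for blood donation, with the study duration and then at least 90 days after the dose. The synopsis puts the whole study at about 8 weeks from screening, or 9 with return visits.

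What is at stake is safety information. With no reproductive or developmental toxicity data, a partner pregnancy after exposure is worth knowing about. The subject is the site's likely source for it, and no contact is scheduled between the last visit and day 111.

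**Working it through.** **1. Reproduce the protocol's 111 days (section 9.4).** Five half-lives: 5 × 98.138 h = 490.69 h; 490.69 / 24 = 20.4 days, rounded up to 21. Then 90 + 21 = 111 days. The stated figure reproduces.

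**2. Days from dosing to the end of the study.**
- Planned discharge on Day 22, 504 h (section 8.1): 504 / 24 = 21 days.
- Extended residency to Day 26, 600 h (section 8.1): 600 / 24 = 25 days.
- Eight weeks from screening (synopsis), with screening 28 days before dosing: 56 − 28 = 28 days.
- Nine weeks from screening, same assumption: 63 − 28 = 35 days.
- Latest scheduled return visit (section 10.3.4): 816 h = 34 days, plus 24 h of collection, plus the 2-day window: 34 + 1 + 2 = 37 days.

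**3. Days with no instruction to notify.** Uncovered days = 111 − study end. Share after dosing = uncovered / 111. Share from consent, with consent 28 days before dosing, = uncovered / (111 + 28) = uncovered / 139.

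| Study ends | Days after dosing | Uncovered days | Share of 111 | Share of 139 |
|---|---|---|---|---|
| Day 22 | 21 | 90 | 81.1% | 64.7% |
| Day 26 | 25 | 86 | 77.5% | 61.9% |
| 8 weeks from screening | 28 | 83 | 74.8% | 59.7% |
| 9 weeks from screening | 35 | 76 | 68.5% | 54.7% |
| Day 35 visit, latest | 37 | 74 | 66.7% | 53.2% |

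The post-dose base suits a risk that comes from drug exposure. The consent base matches the formal start of the contraception requirement in 9.4. The gap is more than half of the window on either.

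**4. What could move the range.** Group release before Day 22 is allowed (section 8.1) and would widen the gap, but the documents give no expected date for it. Home collections after the return visits have no stated end and would narrow it. The table also takes the subjects as dosed at about the same time, since section 18.5 defines the end by the last subject.

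**The case against.** The best counter-argument is the third sentence of 9.5. It has no end date, it applies to a pregnancy found at any time after inclusion, and the closing line on the form and follow-up is not time-limited either. A reader might infer from the gap that mother and child would go without follow-up. The documents do not support that: once a pregnancy is known, follow-up is provided for, subject to the partner's consent. What survives is narrower. That sentence acts on a pregnancy already found and does not tell the subject to report one.

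A post-study safety route also exists in part. Section 14.4.1 counts a congenital anomaly as a serious event, and section 16.1 allows expedited reporting of serious events after completion if the sponsor judges them to be SUSARs. That route too depends on someone telling the site.

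The consent pages are not among the documents reviewed, so the participant information may already state a longer period. The point is therefore about the protocol text.

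Two further inferences go too far. One is that 67% to 81% of pregnancies would be missed: the figures are shares of days, and they do not convert to shares of conceptions. The other is that these pregnancies would be the only human information on the risk. Section 5.3.2 lists other completed and ongoing rencofilstat studies, and the documents do not say whether those collect pregnancy data.

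The scale is also small: six men, a single dose, and a condom plus a highly effective method where the partner could conceive.

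**Conclusion.** The mismatch between 9.4/9.4.1 and 9.5 is real. Followed exactly, 9.5 leaves 74 to 90 of the 111 post-dose days (67% to 81%) without an instruction to notify the investigator, or about 53% to 65% of the window counted from consent. This rests on the planned schedule, a study end 21 to 37 days after dosing, and, for the consent-based share, consent 28 days before dosing. Home collections would reduce the gap and earlier group release would increase it.

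The defect is confined to the prompt to report; follow-up of a known pregnancy is already covered. It is a safety-reporting gap that is worth closing because the protocol itself set the longer period. It has no bearing on the mass balance or PK analyses.

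**What to change.** Reconcile 9.5 with 9.4 by extending the reporting period. In both reporting sentences, keep the reference to the study and add the time up to 111 days after IMP administration. Replacing the present wording with a window that starts at dosing would be a mistake, because it would drop the existing cover between entry to the study and dosing, whereas the 9.4 period starts at consent.

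State that the notification form and follow-up apply to any conception in the extended period. Repeat the instruction in the participant information and on the contact card that subjects already receive under section 10.3.5.

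No visit or procedure is added. The site and sponsor must keep the pregnancy reporting route open until 111 days after dosing. The change to the participant information goes through section 17.1; if the amendment is substantial, that means submission to the MHRA and/or ethics committee as required, notice to the ARSAC practitioner and re-consent of enrolled subjects.

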9.6 Additional Study Restrictions

The following additional restrictions will be in place for the duration of the study:

- 1. Subjects must abstain from alcohol during the 24 h prior to screening and the 24 h prior to admission until discharge from the clinical unit
- 2. Subjects must not drink liquids or eat food containing grapefruit, cranberry, caffeine or other xanthines from 24 h prior to admission until discharge from the clinical unit
- 3. Subjects should refrain from eating food containing poppy seeds for 48 h prior to screening and for 48 h prior to admission until discharge from the clinical unit
- Subjects must not take part in any unaccustomed strenuous exercise from the 72 h before the screening visit and then from 72 h prior to admission until discharge from the study
- 5. Must not donate blood or plasma (outside of this study), from screening, throughout the study duration, and for at least 90 days following dose of IMP
- 6. Due to the unavailability of phototoxic data for rencofilstat, subjects will be advised to minimise exposure to sunlight by spending a reduced amount of time outdoors/remaining inside the clinical unit during the residential periods of the study, wearing sunglasses and clothing that minimises exposure to sunlight and using sun cream on exposed areas when going outdoors. They will also be advised not to use sunbeds. This restriction will be advised from dosing until 7 days post-dose

7. Subjects will not be permitted to shower for 24 h post-dose (to ensure the collection of all samples)

The additional restrictions above are not exclusion criteria; if non-compliance occurs, a protocol deviation will be completed.

10 Study Procedures

Study procedures will be performed as detailed in the study schedule of assessments in Appendix 2, and in accordance with Quotient's standard operating procedures (SOP)s unless otherwise stated in this protocol.

10.1 Screening

Within the 28 days preceding dosing, all subjects will be required to undergo a screening visit. Screening procedures will be carried out in accordance with the schedule of assessments in Appendix 2.

If the start of the study is delayed for any reason so that the interval between screening and dosing exceeds 28 days, all or part of the screening procedures will be repeated at the discretion of the investigator.

Screening safety procedures such as safety bloods, ECGs, vital signs, carbon monoxide breath tests, alcohol breath tests and urinalysis can be repeated as clinically indicated under the discretion of the investigator or sub-investigator if there is a concern regarding a subject's safety or eligibility to participate in the trial.

10.1.1 Subject Re-Screening

This study permits the re-screening of a subject who has discontinued the study as a pre-treatment failure (ie subject has not been treated); the reason for failure must be temporary and expected to resolve. If re-screened, the subject must be re-consented.

10.2 Admission and Pre-dose Procedures

The identity of the subjects will be confirmed at admission and pre-dose.

In addition, the ongoing eligibility of subjects will be re-assessed at admission/pre-dose, as described in Sections 9.2 and 9.3.

Admission/pre-dose safety procedures such as safety bloods, ECGs, vital signs, urinalysis and drugs of abuse tests can be repeated as clinically indicated under the discretion of investigator or sub-investigator if there is a concern regarding a subject's safety or eligibility to participate in the clinical trial.

If dosing is delayed, subjects who have completed admission procedures do not need admission procedures to be repeated if dosing is within 2 days and the subjects have remained resident in the clinical unit.

The subjects will be admitted to the clinical unit on the evening before dosing (Day -1).

In addition, subjects may be required to visit the clinical unit on Day -1 prior to admission to the clinical unit for SARS-CoV-2 antigen tests (if required; see Sections 6.4.3.2 and 14.5.7). Test results must be available prior to dosing.
The admission and pre-dose procedures are presented in Appendix 2.

10.3 Study Day Procedures

10.3.1 Blood Volume

The total blood volume for each subject will not exceed 550 mL in a 4-week period.

The first 0.5 mL of blood withdrawn via cannula will be discarded.

10.3.2 Timing of Procedures

There are times where the protocol requires more than one procedure to be completed at the same time point. In these instances, the following will apply to post-dose time points:

- PK samples should take priority over other procedures scheduled at the same time point
- ECGs should be taken prior to vital signs when both measurements are scheduled at the same time point
- Other assessments, eg physical examinations, will be performed within the required time windows

As guidance, the preferred order of assessments is:

All safety assessments will be timed and performed relative to the start of dosing.

10.3.3 Discharge from the Clinical Unit

A subject will be allowed to leave the premises without additional investigator or sub-investigator review, following completion of study-specific procedures providing that:

- No AEs have been reported during the study visit
- The subject responds in the affirmative when asked if they are feeling well

Refer to Section 8.1 for further details of subject discharge.

If any of these conditions are not met, then the subject will only be allowed to leave the clinical unit with the authorisation of the investigator or sub-investigator.

There will be no continued provision of the study intervention or treatment for subjects as this study involves healthy volunteers only.

10.3.4 Return Visits

If the mass balance criteria have not been met by the morning of Day 26, subjects not achieving the release criteria may be required to return to the clinical unit for up to 2 return visits on Day 28 (+2 days; 648 h post-dose) and (if mass balance criteria are still not met by Day 28) Day 35 (±2 days; 816 h post-dose) for 24-h faeces and/or urine collections as described in Appendix 2.

Refer to Section 8.1 for further details.

10.3.5 Medical Supervision

A physician will be responsible for the clinical aspects of the study and will be available at all times during the study. In accordance with the current Association of the British Pharmaceutical Industry guidelines [18], each subject will receive a card stating the telephone number of the investigator and the 24/7 contact details of the Quotient's on-call physician.

11 Dosing of Subjects

11.1 Food and Fluid Intake

Subjects will be allowed water up to 1 h before the scheduled dosing time and will be provided with 240 mL of water at 1 h post-dose (to ensure adequate hydration), and thereafter water will be allowed ad libitum after 1 h post-dose. Decaffeinated fluids will be allowed ad libitum from lunch time on the day of dosing.

If, for technical reasons, dosing is delayed for more than 2 h beyond the expected dosing time, subjects will receive 200 mL of an electrolyte drink (eg Lucozade Sport) at the originally scheduled dosing time, or earlier if possible.

The calorie/fat content of meals are not required to be controlled. Subjects will be provided with a standardised menu.

Subjects will be provided with a light snack and then fast from all food and drink (except water) for a minimum of 8 h on the day prior to dosing until approximately 4 h post-dose at which time lunch will be provided. An evening meal will be provided at approximately 10 h post-dose and an evening snack at approximately 14 h post-dose. On subsequent days, meals will be provided at appropriate times.

If an individual subject has not experienced a bowel movement in any 36 h period post-dose, fluid intake should be increased and administration of a mild laxative (eg prune juice or a mild stool softener) should be implemented.

11.2 Administration of Test Preparations

Specific details of the IMP and doses to be administered are provided in Section 5.2 and Section 8.1, respectively. Subjects will be dosed on the morning of Day 1.

The exact time of dosing will be decided based on logistics and will be documented in the source.

Subjects will receive 1 single administration on a single occasion.

Immediately after administration of the oral emulsion, the dosing vessel will be rinsed with water and subjects will consume the rinse solution. Subjects will then consume further water to a total volume of 240 mL (including the dosing volume and volume used to rinse the dosing vessel).

11.3 Dosing Compliance

During all clinical phases of the study, subjects will be observed by study staff to assure compliance to all study procedures, including dose administration.

Mouth checks will be conducted after dosing to ensure the emulsion has been swallowed.

The date and time that each subject is dosed will be recorded in the subject's source data. Any violation of compliance will require evaluation by the investigator and sponsor to determine if the subject can continue in the study.

11.4 Prior and Concomitant Medications

No prescribed, over-the-counter medication or herbal remedies will be permitted from 14 days before IMP administration until discharge from the study except up to 4 g of paracetamol per day and those deemed necessary by the investigator to treat AEs (see also Section 9.3).

In addition, no strong or moderate CYP3A4 inducers will be permitted from 30 days before IMP administration until discharge from the study.

Any medications used will be recorded in the source.

Subjects are not permitted to receive the COVID-19 vaccine within 7 days prior to administration of IMP, so that by the time of dosing any effects of the vaccine (eg, pyrexia, fatigue, pain/stiffness at site of injection) are likely to have abated. Subjects will be permitted to have the vaccination when discharged from the clinical unit.

Emergency equipment and drugs will be available within the clinical unit as per current standard procedures. In the unlikely event that they are required, their use will be documented.

12 Assessment of Efficacy

Not applicable for this Phase I study.

13 Assessment of Mass Balance, Pharmacokinetics, Metabolite Profiling and Identification, and Pharmacodynamics

